2.5 Rationale for choice of comparators drugs

Not applicable

2.6 Risks and benefits

Appropriate eligibility criteria, as well as specific dose delays and stopping rules are included in this protocol. Recommended guidelines for prophylactic or supportive management of study-drug induced adverse events are provided in [Section 6](#). The risk to subjects in this trial may be minimized by compliance with the eligibility criteria and study procedures, close clinical monitoring, and stopping rules.

Infusion of drugs such as PDR001 and /or LAG525 can be associated with reactions especially during the first exposure. Infusion reactions usually consist of symptoms such as fever, chills, nausea, vomiting, headache, dizziness, dyspnea, hypotension, rash, and asthenia.

PDR001: The most frequent side effects caused by single-agent PDR001 include: diarrhea, nausea, vomiting, constipation, gastritis, hypothyroidism, hyperthyroidism, itchiness, skin reactions (such as rash, dryness, redness, hives), low red blood cell count, dry mouth, inflammation in the mouth, canker sores, loss of appetite, decreased blood sodium, increased blood sugar, pain in joints, muscles, nerves & skin, swelling in the face or limbs, pneumonia, abnormal liver function tests, increased lipase, decreased lymphocytes, weight loss, fever, chills, malaise, weakness, fatigue, abdominal discomfort and pain, shortness of breath during exercise or at rest, cough, vertigo/dizziness, and headache.

Less frequent side effects caused by single agent PDR001 include the following severe immune reactions: colitis requiring hospitalization; pneumonitis & pneumonia, hepatitis with abnormal liver test results; and polymyositis with muscle weakness,

LAG525: The most frequent side effects caused by single-agent LAG525 include: fatigue, nausea, vomiting, fever, abnormal liver function tests, loss of appetite, joint and muscle pain, itchiness, skin reactions such as rash, dryness, redness & hives, hypothyroidism, increased amylase, increased lipase, hyperkalemia, hyperuricemia, constipation, dry mouth, lack of energy, abdominal pain, diarrhea, and weight loss.

One case of acute kidney injury possibly related to LAG525 occurred in the setting of widespread metastatic disease, tumor lysis syndrome, and multiple organ failure leading to death. Kidney function is evaluated in all patients regularly throughout this study.

Combination of PDR001 and LAG525: While the incidence of immune related adverse events with single agents has been well characterized, there may be a higher incidence of immune related adverse events with combination immune therapies including the combination of PDR001 and LAG525. These adverse events may be serious and include, but are not limited to, allergic reactions, inflammation of the heart, pneumonitis, colitis, diabetes, hepatitis, and other autoimmune disorders, increased phosphate, distortion of taste, flatulence, flushing, and headache.

The combination of PDR001 and LAG525 is hypothesized to improve upon responses to single-agent anti-PD-1/PD-L1 therapies. The ongoing study, LAG525X2102C, A Phase I/II, open-label, multicenter study of the safety and efficacy of LAG525 single agent and in combination with PDR001 administered to patients with advanced malignancies, provides encouraging data on the tolerability and response rate of this combination treatment, lending support to this hypothesis.

Therefore, the potential benefit of combination therapy with PDR001 and LAG525 is thought to outweigh the risk in those patients with advanced malignancies and minimal therapeutic options who are still eligible by standard criteria for participation in clinical trials.

For additional information on risk-benefit assessment, please refer to [PDR001 Investigators Brochure] and [LAG525 Investigators Brochure].

3 Objectives and endpoints

Objectives and related endpoints are described in Table 3-1 below.

Table 3-1 Objectives and related endpoints

Objective	Endpoint	Analysis
Primary	Assess CBR at 24 weeks of PDR001+LAG525 by tumor type in multiple solid and lymphoma	Refer to Section 10.4 The primary objective is to assess clinical benefit rate after 24 weeks of treatment with PDR001+LAG525 based on local investigator assessment. For patients with solid tumors the assessment criteria will be RECIST 1.1 and will include responses of CR or PR or SD. For lymphoma, assessment criteria will be the Revised Response Criteria for Malignant Lymphoma, (Cheson et al 2007).
Secondary	Assess ORR by RECIST 1.1 in solid tumors and by the Revised Response Criteria for Malignant Lymphoma (Cheson et al 2007) in lymphoma TTR, DoR, TTP, PFS/ rate at 1 and 2 years Safety incidence and severity of adverse events (AEs) and serious adverse events (SAEs) including changes in laboratory parameters, vital signs and ECGs Tolerability: Dose interruptions, reductions and dose intensity.	Refer to Section 10.5 . To assess Overall Response (OR) of Partial Response (PR) or Complete Response (CR) based on local investigator assessment. Time to response (TTR) is defined as the time from the date of first dose to the date of first documented response of CR or PR. The duration of response (DOR) applies only to patients whose best response was PR or CR. The duration of response is defined as the time from the first documented response to the date first documented disease progression or relapse or death due to any cause. The duration of response will be summarized descriptively for each tumor cohort. Time to progression (TTP) is defined as the time from the date of first dose to the date of first documented disease progression or relapse. Progression free survival (PFS) is defined as the time from the date of first dose to the date of first documented disease progression or relapse or death due to any cause.

4 Study design

4.1 Description of study design

This is a phase II, open-label study to determine the efficacy and safety of treatment with the combination of PDR001+LAG525 across multiple tumor types that are relapsed and/or refractory to available standard of care therapies (Table 4-1).

Table 4-1 Tumor Cohorts

Group	Malignancy
1	Small cell lung cancer
2	Gastric/esophageal adenocarcinoma
3	Castration resistant prostate adenocarcinoma (CRPC)
4	Soft tissue sarcoma
5	Ovarian adenocarcinoma
6	Advanced well-differentiated neuroendocrine tumors*
7	Diffuse large B cell lymphoma (DLBCL)*

*Please refer to [Section 5](#) for disease specific inclusion/exclusion

Tumor cohorts may be excluded during the course of the study in the case of early futility or success based upon interim analyses or at the discretion of Novartis. Additional tumor cohorts may be added at the discretion of Novartis based on emerging pre-clinical or clinical data.

[figure not shown]
Patients will receive study treatment for a maximum of 2 years, or until disease progression (assessed by investigator per RECIST 1.1 or the Revised Response Criteria for Malignant Lymphoma criteria (Cheson et al 2007)), unacceptable toxicity, death or discontinuation from study treatment for any other reason (e.g., withdrawal of consent, start of a new anti-neoplastic therapy or at the discretion of the investigator or patient). All patients who discontinue from study treatment due to disease progression must have their progression clearly documented. All disease assessments will be performed locally by the investigator.

Radiological disease assessments will be performed every 6 weeks (± 7 days), starting 12 weeks after first dose of study drug and continuing through week 24. The frequency of radiological disease assessments will be reduced to every 12 weeks after patients have completed 24 weeks on treatment and will continue until confirmed disease progression. Additional response assessments may be performed at the discretion of the investigator.

4.2 Enrollment model

[figure not shown]
This study is intended for patients who have a pathologically confirmed diagnosis of any tumor listed in [Table 4-1](#), and have relapsed and/or refractory disease. Once the patient has been identified, treating physicians who are qualified investigators may contact Novartis or designee to consider enrollment in the appropriate tumor cohort. Informed consent must be signed before any screening activities take place. If all eligibility criteria are met (see [Section 5](#)), the patient will initiate therapy with the combination of PDR001 and LAG525. The patient may not receive any additional anti-cancer therapy during treatment with PDR001 and LAG525.

A schematic representation of the study start-up design is shown in Figure 4-1.

Figure 4-1 Study Start-up Design

4.3 Tumor cohort enrollment schema

Accrual to each tumor cohort will consist of a futility and expansion stage based on the observed 24 week CBR rates. The 24 week CBR rate will be continually assessed for futility and early success by comparing posterior quantities for the rate to pre-specified futility and expansion criteria for each cohort (see [Section 10](#)). Analysis for both futility and expansion will borrow information across cohorts with a hierarchical model (see [Section 10](#)). The hierarchical model allows dynamic borrowing of information between cohorts such that more borrowing occurs when the cohorts are consistent and less borrowing occurs when the cohorts differ. In this way, the model is a compromise between the two alternate extremes of either a completely pooled analysis or a separate analysis in each cohort. We additionally incorporate a clustering mechanism that allows borrowing within clusters but treats clusters separately. This minimizes borrowing across cohorts that are quite different in terms of CBR.

Figure 4-2 Study Design

Depending on whether or not pre-specified criteria for stopping (for futility) or continuing enrollment (for early success) is met, each tumor cohort can enroll a minimum of 5 patients and a maximum of 30 patients during the course of the study. When at least 5 patients within a group have completed 24 weeks of treatment and have CBR data available, analysis for futility and early success (expansion) will commence to inform a “go/no-go” decision for that cohort. For tumor cohorts in which treatment is not declared futile and pre-specified CBR rate for early success is met, a “go” decision will be made to continue enrolling to a maximum of 30 patients for that cohort. Expanded tumor cohorts will continue to have ongoing analysis for futility to allow for early stopping in the event that observed 24 weeks CBR rates do not meet pre-specified final success criteria (see [Section 10](#)). For tumor cohorts in which treatment has not been declared futile, but criteria for expansion has not been met, enrollment will be paused at 10 patients until a “go/no-go” decision can be made based on information gleaned from the dynamic borrowing of CBR data across tumor cohorts (see [Section 10](#)). A “no-go” decision can be made for a tumor cohort if: 1) 24 week CBR rates of the first 5-10 patients show treatment to be futile and cohort will not expand; 2) subsequent analysis in a cohort that expanded fails to demonstrate continued evidence of activity such that 24 weeks CBR is not predicted to meet pre-specified criteria for final success (See [Section 10](#)).

Primary analysis for all stages will be intent-to-treat. Those patients who discontinue study treatment for any reason other than disease progression or treatment related toxicity may be replaced (at the discretion of Novartis), until at least 5 patients with 24 weeks of CBR data are accrued within a cohort. All patients enrolled into a tumor cohort prior to expansion must not have been exposed to prior immuno-oncology (IO) therapy as specified in exclusion criteria ([Section 5.3](#)).

Once a tumor cohort is selected for expansion, the cohort shall continue to enroll patients until the cohort enrolls a total of 30 patients.

In each expansion cohort, it is permissible to enroll patients that have received previous CPB therapy as follows:

- A maximum of 6 of the 30 patients enrolled into an expansion cohort may have received previous CPB therapy.
- All patients enrolled prior to expansion must be IO naive
- 24 of the 30 patients enrolled into each tumor cohort must be IO naive.
- In the event an expanded cohort does not enroll 30 patients, the previously treated patients must not comprise more than 20% of total number of patients enrolled in the cohort.
- The patients previously exposed to CPB therapy must satisfy all inclusion-exclusion criteria as set forth in sections 5.3 and 5.4

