7.1.5.1 Replacement policy

Those patients who discontinue study treatment for any reason other than disease progression or treatment related toxicity may be replaced at the discretion of Novartis, until a minimum of 5 patients with 24 weeks of CBR data are accrued within a cohort.

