6.1 Simulation Assumptions

6.1.1 Trial Enrollment

The assumed average accrual is 124 subjects in 18 months across the 7 groups. The average group rate of accrual varies by group, with some groups enrolling at a faster rate than others. Hypothetical yearly accrual rates are provided in Table 1. It is anticipated that the yearly accrual rates will vary by group, but based on a different pattern across groups than that assumed for simulations. A Poisson distribution with these assumed mean rates dictate trial entry for simulated subjects. Hence, actual accrual rates within each simulated trial will vary from the mean based on this distributional assumption.

No dropouts are assumed for this simulation; hence, the final endpoint will be observed for every subject.

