6.4 Example Trials

6.4.1 Overview

In this section, we present an example of the trial to illustrate the adaptive process.

The trial is described graphically in a series of plots. Each plot describes the current data at the time of the interim. The plots include the following features:

- Light gray bars represent the number of subjects enrolled.
- Dark gray bars represent the number of subjects with CBR data
- Bars may be outlined blue, yellow, red, or green. Blue indicates a group may continue to enroll; yellow indicates that enrollment has been paused for the group; red indicates a group has permanently stopped for futility; and green indicates a group has declared success.
- Vertical dashed lines are provided at 10 and 24 subjects.
- Text columns to the right of the plot display the following summary statistics for each group:
 - Pr(>Ctrl): The probability that the CBR exceeds that group's corresponding historical control based on the hierarchical model
 - Data: The observed number of events/the number of subjects with CBR data available
 - Obs. CBR: The observed CBR

- Est. CBR: The model-estimated CBR
- Red/green diamonds at n=10 indicate whether a group has met its expansion threshold (no go/go). Once a group has expanded beyond n=10, this gate remains green.
- The historical control for each group is displayed on the left side in orange.

In the simulations, interims occur every 13 weeks. Hence, a large number of interims may occur per trial. For this example, we show results for a small number of select interims in order to highlight the features of the adaptive design.

6.4.2 Example Trial 1

6.4.2.1 Example Trial 1, Interim 1

The trial begins enrolling subjects across all groups. The first interim analysis (Figure 12) occurs at 31 weeks from the first subject enrolled. Decisions (for futility or sample size expansion) can only be made for groups that have at least 5 subjects with CBR data available. No groups have CBR data available from at least 5 subjects, and therefore, no groups can stop for futility or enroll beyond 10 subjects until the next interim analysis. Groups 2 and 3 have already enrolled 10 subjects and therefore pause enrollment. This enrollment pause will be re-evaluated at the next interim analysis.

[figure not shown]

Figure 12 – Example trial 1, interim 1

6.4.2.2 Example Trial 1, Interim 2

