2.5.3 Handling of missing values/censoring/discontinuations

For the computation of CBR (CR, PR or SD) in case of solid tumor all confirmed responses (CR or PR) reported up to the analysis cut-off will be included. Patients with no valid radiological assessment or unconfirmed responses will be considered as non-responders. In particular, patients with CR or PR at the last radiological assessment prior to cut-off and no response at the previous assessment are by definition unconfirmed and will be considered as non-responders for the primary analysis.

Patients with unknown or missing BOR will be counted as failures (non-responders). If there is no baseline tumor assessment, all post-baseline overall lesion responses are expected to be 'Unknown'. If no valid post-baseline tumor assessments are available, the BOR must be

‘Unknown’ unless progression is reported. For the computation of CBR, these patients will be included in the FAS and will be counted as ‘non-responders’.

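### The plan does not settle whether replaced early leavers stay in the CBR denominator; if they are dropped, the first go/no-go decision can be biased toward expansion

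*Protocol*

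**What the plan says.** **Replacement.** Protocol 4.3, 7.1.5.1 and SAP 1.1.3 carry the same rule. In 4.3 it reads: "Those patients who discontinue study treatment for any reason other than disease progression or treatment related toxicity may be replaced". The choice lies with the sponsor. Section 7.1.5.1 sets the limit: "until a minimum of 5 patients with 24 weeks of CBR data are accrued within a cohort". Reasons in Protocol 7.1.5 that can qualify include an unrelated adverse event, physician or patient decision, loss to follow-up, and death from another cause.

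**Texts that keep such a patient in the count.**
- Protocol 4.3, in the sentence before the rule: "Primary analysis for all stages will be intent-to-treat".
- Protocol 10.1.1 puts every dosed patient in the FAS, with no exception for replaced patients.
- SAP 2.5.3: "Patients with unknown or missing BOR will be counted as failures (non-responders"; it keeps patients without a valid tumor assessment in the FAS for CBR.

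**Texts that point to an evaluable-only count.**
- Protocol 4.3 starts the go/no-go analysis as follows: "When at least 5 patients within a group have completed 24 weeks of treatment and have CBR data available".
- SAP 2.2.1 removes treated patients without any post-baseline assessment from the FAS. The first scheduled scan is at week 12 (Protocol 4.1). SAP section 4 declares that the FAS definition was changed but does not reconcile it with SAP 2.5.3.

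**Simulation.** Appendix 4, section 6.1.1: "No dropouts are assumed for this simulation".

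**The concern.** In relapsed cancer, a patient who stops early for a reason not recorded as progression or drug toxicity may still be deteriorating. If that patient is replaced and leaves the denominator, the first futility and expansion decision describes CBR among patients who stayed evaluable, not among all treated. The historical rates come from median PFS (Appendix 4, section 6.1.2), and PFS as the protocol defines it counts death from any cause as an event. The trial rate would then omit some failures that the benchmark includes. Whether to replace is decided by a sponsor who can see the data, and the vendor running the interims could follow either set of texts.

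**Working it through.** **1. Reproduce the plan's figures.** The historical rate is R = 0.5^(6 / median PFS in months). Medians of 1.5, 3, 4, 5 and 6.2 months give 6.25%, 25%, 35.4%, 43.5% and 51.1%, as in Protocol Table 10-1. The full borrowing design was re-simulated from Appendix 4 (1,000 trials per scenario; Dirichlet process with α = 2; μ variance 1.82; τ² ~ IG(3, 0.5); thresholds 0.20, 0.70, 0.60 and 0.80). The chance of any false success in All Null is 0.422, against 0.431 in the plan. Average trial size is 95.2 against 94.3 in All Null, and 151.7 against 150.6 in All Great.

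**2. Assumption.** The documents give no rate d of replaceable discontinuation. I take d = 10%, with 20% as a wider case. For the upper bound every leaver is a failure. If the true CBR over all treated patients equals R, the rate among those who stay is R/(1 − d).

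**3. First look without borrowing, five patients.** The prior is θ ~ N(0, 1.82 + 0.25), where 0.25 = 0.5/(3 − 1) is the mean of IG(3, 0.5). The smallest count out of 5 with Pr(π > R) above 0.70 is the cut-off. Reading 1.82 as a standard deviation leaves all cut-offs unchanged.

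| Cohort | R | Cut-off (posterior) | Pass, leavers kept (rate R) | Pass, leavers dropped, d = 10% |
|---|---|---|---|---|
| Gastroesophageal, NET | 43.5% | 3/5 (0.74) | 0.38 | 0.47 |
| Ovarian, DLBCL | 25% | 2/5 (0.71) | 0.37 | 0.43 |
| STS | 51.1% | 4/5 (0.88) | 0.20 | 0.28 |
| Prostate | 35.4% | 3/5 (0.83) | 0.24 | 0.31 |
| SCLC | 6.25% | 1/5 (0.73) | 0.28 | 0.30 |

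For R = 43.5%, kept: 10(0.435³)(0.565²) + 5(0.435⁴)(0.565) + 0.435⁵ = 0.379. Dropped, at 0.435/0.9 = 0.483: 0.469.

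For R = 25%, kept: 1 − 0.75⁵ − 5(0.25)(0.75⁴) = 0.367. Dropped, at 0.25/0.9 = 0.278: 0.426.

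**4. Full design with borrowing, no true effect (800 trials per replacement run).** Leavers stop at week 12. Each is replaced and removed while fewer than 5 patients in the cohort have data; later leavers count as failures.

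| Handling | Mean expansion probability | Mean group false success | Any false success |
|---|---|---|---|
| No dropouts | 0.331 | 0.090 | 0.422 |
| 20% leave, kept as failures | 0.317 | 0.093 | 0.421 |
| 10% leave, removed | 0.445 | 0.143 | 0.551 |
| 20% leave, removed | 0.577 | 0.194 | 0.664 |

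Keeping leavers as failures preserves the stated error rate. Removing them does not.

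**5. Lower end.** If leaving is unrelated to outcome, the rate among those who stay is still R, and the no-dropout row applies.

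**The case against.** The strongest reply is that no text removes a replaced patient from the CBR count. Replacement can simply mean enrolling one more patient. Read with the intent-to-treat sentence, the protocol FAS and SAP 2.5.3, the replaced patient stays as a failure, and the 5-patient condition only fixes timing. This stands against the stronger inference that the go/no-go certainly rests on evaluable patients, or that the replacement rule cannot coexist with intent-to-treat. Read literally, the trigger would also leave out patients who stopped early for progression, so it is at most a hint about the denominator.

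Three other tempting inferences also fail.
- The Appendix 4 label "Data: The observed number of events/the number of subjects with CBR data available" describes example plots from a simulation without dropouts. There it separates patients with follow-up from those still pending, and it sets no rule for early leavers.
- Not every replaced patient is a failure. SAP 2.5.2 counts stable disease within the first 24 weeks as benefit, so a patient stable at week 12 who then leaves by choice is a success, and dropping that patient lowers CBR.
- Deterioration does not always escape the count. SAP 2.5.2 treats progression given as the reason for stopping, or as the cause of on-treatment death, as progressive disease.

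SAP 2.2.1 also does not say that its assessment must be a tumor assessment. If any visit qualifies, few patients are lost. Finally, a pause can be lifted and an expansion stopped at later interims.

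What the reply does not remove is that SAP 2.2.1 excludes some dosed patients whom Protocol 10.1.1 includes. If it means tumor assessments, it also contradicts SAP 2.5.3 and drops those who leave before the week-12 scan.

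**Conclusion.** The concern holds as a conflict over the denominator, not as proof that replaced patients are excluded. The documents contain both a keep-as-failure rule and wording that supports an evaluable-only count, for a discretionary decision that opens or closes each cohort. If leavers are dropped and leaving is linked to poor outcome, the bias favours expansion, and the operating characteristics in Appendix 4 do not cover it. The 10% figures in the working are upper bounds: they need every leaver to be a failure and, in the re-simulation, every eligible leaver to be replaced and removed. The true effect could lie anywhere between that bound and none, and removing patients with earlier stable disease could reverse its direction. The plan should be corrected because the remedy is cheap and the affected decision is central.

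**What to change.** In Protocol 4.3, 7.1.5.1 and SAP 1.1.3, state that:
- every dosed patient, including any who is replaced, stays in n at every interim and at the final CBR analysis;
- the patient is classified by the plan's own CBR definition, and is a non-responder (Y = 0) when no qualifying response exists;
- the patient counts as having CBR data, and so toward the 5, once that status is determined, with the trigger wording in 4.3 aligned;
- replacement only adds patients to the cohort.

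Delete the SAP 2.2.1 sentence that excludes patients without a post-baseline assessment, so that it agrees with Protocol 10.1.1 and SAP 2.5.3.

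The cost is a few sentences and one data-handling rule for the interim vendor. Interim CBR will be slightly lower and somewhat fewer cohorts will expand. There is no need to delete the replacement clause or change the list of replaceable reasons.
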